7.22.1.3 Infusion/Hypersensitivity Reactions and Management

Infusions of proteins can be associated with reactions to the infusion that may or may not be immune-mediated (hypersensitivity reactions). Thus, potential reactions to the infusion of investigational drug are unpredictable. It is often difficult to clinically distinguish infusion reactions from hypersensitivity reactions. Symptoms may include headache, fever, sensory paresthesias (including feeling of warmth, tingling, or pain), rash, pruritus, or autonomic symptoms, such as dry mouth or gustatory abnormalities (including loss of smell and metallic taste). Changes in mental status or level of consciousness that are not caused by pre-medication may either occur acutely or develop post-injection over time.

The management of infusion reactions and hypersensitivity reactions is similar. The following steps may be taken, at the discretion of the investigator, in the event of a suspected infusion related/hypersensitivity reaction and the management of such reactions should be based on the severity of the reaction:

- Treatment with medications such as antihistamines, antipyretics, and/or corticosteroids
- Stopping and resuming treatment
- Pretreatment with antihistamines and/or corticosteroids may prevent subsequent reactions in those cases where symptomatic treatment was required

7.22.1.4 IDDD-related Adverse Events

IDDD ADVERSE EVENTS

Examples of AEs related to use of the IDDD include, but are not limited to, the following: device failure, device malfunction, incorrect connection of IDDD components, erosion of the portal/catheter through the skin, fibrin sheath formation around the catheter tip, hematoma, implant rejection, migration of the portal/catheter, occlusion of the portal/catheter, portal site, or subcutaneous tract infection. The device may also need to be replaced or repaired as needed. A malfunction of the device (defined in Section 7.22.2.2) should not be entered as an AE unless it has physiological consequences. In the event of a device failure (defined in Section 7.22.2.3), the device may need to be replaced or repaired. Hospitalization for such a procedure will be reported as a serious adverse event (SAE). Details of the cause of IDDD malfunction or failure will be recorded on the Device Malfunction/Failure CRF. A list of the more common IDDD AEs is included in [Appendix 3](#).

DEVICE SURGICAL PROCEDURE-RELATED ADVERSE EVENTS

Examples of AEs related to device surgical procedures include, but are not limited to, the following: events that occur during or following IDDD implant/explant, IDDD adjustment, full revision, partial revision, IDDD removal, and delayed re-implantation after previous IDDD removal (such as complications of anesthesia, excessive bleeding, wound hematoma) and post operative complications (such as post-operative infection).

IT ADMINISTRATION PROCESS ADVERSE EVENTS

Intrathecal administration process AEs include those caused by anesthesia during drug administration, drug administration issues (eg, extravasation during infusion or hematoma due to Huber needle) or complications of lumbar puncture.

RISKS ASSOCIATED WITH ANESTHESIA REQUIRED FOR STUDY ASSESSMENTS

The use of an IDDD has been chosen to minimize the risks inherent in utilizing novel delivery systems and to alleviate the need for multiple administrations of anesthesia required for drug injection via repeated LP. The risks from anesthesia include respiratory depression, aspiration, cardiac events, hypoxia, hypotension and hypertension, difficult intubations and extubations, stroke, rapid changes in body temperature, laryngospasm or laryngeal edema, allergic reaction, and death. Patients will be closely monitored for changes in vital signs and related events.

RISKS ASSOCIATED WITH LUMBAR PUNCTURE

Risks associated with LP include pain at the injection site, infection, meningitis, encephalitis, cerebritis, failed procedure, bleeding, dural tears, spinal headache, spinal fluid leakage, nerve damage, and focal and non-focal neurological injury (including paralysis). Patients may require anesthesia prior to an LP. Risks from anesthesia are discussed separately in this section (Section 7.22.1.4).

7.22.1.5 Serious Adverse Event

1. An SAE is any AE occurring at any dose of investigational drug or at any procedure that results in any of the following outcomes:

- Death
- Is life-threatening
- Requires inpatient hospitalization
- Requires prolongation of existing hospitalization
- A persistent or significant disability or incapacity
- A congenital anomaly or birth defect

Important medical events that may not result in death, be life-threatening, or require hospitalization may be considered an SAE when, based upon appropriate medical judgment, they may jeopardize the patient and may require medical or surgical intervention to prevent one of the outcomes listed in this definition. Examples of such medical events include allergic

bronchospasm requiring intensive treatment in an emergency room or at home, blood dyscrasias or convulsions that do not result in inpatient hospitalization. Hospitalizations, which are the result of elective or previously scheduled surgery for pre-existing conditions, which have not worsened after initiation of treatment, should not be classified as SAEs. For example, an admission for a previously scheduled ventral hernia repair would not be classified as an SAE; however, complication(s) resulting from a hospitalization for an elective or previously scheduled surgery that meet(s) serious criteria must be reported as SAE(s). *Furthermore, this does not apply to device failures resulting in scheduled surgical revisions, which should be reported as SAEs.*”

2. Unanticipated Adverse Device Effect (UADE) - Any serious adverse effect on health or safety or any life-threatening problem or death caused by, or associated with, a device, if that effect, problem, or death was not previously identified in nature, severity, or degree of incidence in the investigational plan or application (including a supplementary plan or application), or any other unanticipated serious problem associated with a device that relates to the rights, safety, or welfare of patients. (21CFR812.3[s] or other regulatory requirements, as applicable).

7.22.2 Device-Associated Definitions

7.22.2.1 Device Revision (Partial and Full)

Partial device revision: surgical revision/replacement of one or more component(s) of the device; other component(s) of the original device remain implanted and are not affected (eg, port revision).

Full device revision: the device is removed (explanted) in its entirety and a completely new device is implanted.

7.22.2.2 Device Malfunction

The device does not perform as intended, based on the description in the device’s IFU, but does not require either a partial or full device revision.

7.22.2.3 Device Failure

The device irreversibly fails to perform as intended and requires either a partial or full device revision or removal.

7.22.2.4 Device Adjustment

Surgery of the device which does not result in partial or complete device revision or removal (eg, surgical exploration only or placement of additional sutures, tissue glue, and/or fascial repair).

7.22.3 Classification of Adverse Events and Serious Adverse Events

The National Cancer Institute Common Terminology Criteria for Adverse Events (NCI CTCAE) version 3.0 grading scale should be referenced when assessing the severity of an AE (see [Appendix 6](#)). If an AE is not described in the NCI CTC, the severity should be recorded based on the scale provided in [Table 7-3](#). The severity of all AEs/SAEs should be recorded on the

appropriate eCRF page. Adverse events are graded as Grade 1, 2, 3, 4, or 5 corresponding, respectively, to a severity of mild, moderate, severe, life-threatening, or death.

Table 7-3 Adverse Event Severity

Severity	Definition
Grade 1 (Mild)	No limitation of usual activities.
Grade 2 (Moderate)	Some limitation of usual activities.
Grade 3 (Severe)	Inability to carry out usual activities.
Grade 4 (Life-threatening)	Immediate risk of death.
Grade 5 (Death related to an AE)	Death

7.22.4 Relatedness of Adverse Events and Serious Adverse Events

Relationship of an AE or SAE to investigational product, device, device surgical procedure, or IT administration process is to be determined by the investigator based on the definitions in [Table 7-4](#):

Table 7-4 Adverse Event Relatedness

Relationship to Product(s)	Definition
Not Related	Unrelated to study drug, device, device surgical procedure, or IT administration process.
Possibly Related	A clinical event or laboratory abnormality with a reasonable time sequence to administration of study drug, device, device surgical procedure, or IT administration process but which could also be explained by concurrent disease or other drugs or chemicals.
Probably Related	A clinical event or laboratory abnormality with a reasonable time sequence to administration of study drug, device, device surgical procedure, or IT administration process unlikely to be attributable to concurrent disease or other drugs and chemicals and which follows a clinically reasonable response on de-challenge. The association of the clinical event or laboratory abnormality must also have some biologic plausibility, at least on theoretical grounds.
Definitely Related	The event follows a reasonable temporal sequence from administration of the medication, device, device surgical procedure, or IT administration process follows a known or suspected response pattern to the medication, is confirmed by improvement upon stopping the medication (dechallenge) and reappears upon repeated exposure (rechallenge). Note that this is not to be construed as requiring re-exposure of the patient to study drug; however, the determination of definitely related can only be used when recurrence of event is observed.

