7.24 Safety-related Study Stopping Rules

If any patient experiences a life-threatening (Grade 4) adverse event or death which is considered by the sponsor to be possibly, probably, or definitely related to study drug **or the IDDD**, or if 2 or more patients experience a Grade 3 adverse event during the trial that is considered by the sponsor to be possibly, probably, or definitely related to the study drug **or the IDDD**, then the site will be instructed to halt further HGT-1410 administration to all patients and the safety data reviewed. Following a review of safety data, the study will be either:

- Resumed unchanged
- Resumed with modifications to the protocol or
- Terminated

Patient safety will be monitored on a continuous basis during this study until the last patient completes his or her last scheduled study visit/assessment.

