10.6 Efficacy, Safety, and Pharmacodynamic Evaluations

10.6.1 Primary Analyses

10.6.1.1 Safety Analysis

In general, safety assessments will be based on all assessments post-baseline. The assessment of safety will be based primarily on the frequency of AEs, and on the frequency of clinically notable abnormal vital sign and laboratory values. Changes from baseline will be calculated by subtracting the baseline value from the post-baseline value.

All enrolled patients who had an IDDD surgical procedure and/or received administration of HGT-1410 will be included in the safety analysis.

Adverse events will be recorded throughout the study and at early termination. Adverse events and medical conditions will be coded using the Medical Dictionary for Regulatory Activities (MedDRA).

Adverse events will be summarized by presenting, for each dose group during the treatment period, the number and percentage of patients having any AE, having an AE in system organ class, and having each individual AE. In addition, those events which resulted in death or were otherwise classified as serious will be presented in a separate listing. The incidence of treatment-emergent adverse events, defined as all AEs from the time of the surgery for IDDD implantation to the last follow up contact, ie, 30 days after the last HGT-1410 administration, (new or worsened from baseline) during the treatment period, will be summarized by system organ class, severity, type of adverse event and relationship to trial medication/procedure.

Treatment-emergent AEs, of the treatment period, deemed related to HGT-1410 administration will be summarized separately.

IDDD and procedure-related AEs will be summarized within system organ class by preferred term. IDDD and procedure-related AEs will be tabulated by severity (mild, moderate, severe) and degree of relatedness. Separate tabulations will be provided for adverse events related to the IDDD, device surgical procedure (including post-implant infections) and IT administration process. These summaries will be presented by device and overall, as appropriate.

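### Table 7-4 applies drug causality criteria to the device, its surgery and the intrathecal procedure, so an irreversible or fatal harm with no other explanation has no defined degree of relatedness

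*Protocol*

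**What the plan says.** Section 7.22.4 sets one scale for four possible sources: "Relationship of an AE or SAE to investigational product, device, device surgical procedure, or IT administration process is to be determined by the investigator", using Table 7-4. The three related rows each ask for reasonable timing plus further conditions:

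- *Possibly*: an event "but which could also be explained by concurrent disease or other drugs or chemicals".
- *Probably*: other causes unlikely, biologic plausibility, and an event "which follows a clinically reasonable response on de-challenge".
- *Definitely*: a response pattern known or suspected for the medication, and an event that "is confirmed by improvement upon stopping the medication (dechallenge) and reappears upon repeated exposure (rechallenge". A note says that re-exposure need not be carried out, but adds that "the determination of definitely related can only be used when recurrence of event is observed".

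*Not Related* means unrelated to any of the four sources.

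The scale is used in the primary safety analysis (10.6.1.1): "IDDD and procedure-related AEs will be tabulated by severity (mild, moderate, severe) and degree of relatedness", with separate tabulations for the device, the device surgery and the IT administration process. The same three labels appear in the stopping rule (7.24), for an event "which is considered by the sponsor to be possibly, probably, or definitely related to study drug" or to the intrathecal device.

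**The concern.** Dechallenge and rechallenge suit a drug that can be stopped and given again. They fit poorly to an implantation, and they cannot be shown for an injury that is permanent or fatal. Appendix 3 lists spinal cord or nerve-root damage among the expected device effects, and section 7.22.1.4 names death among the risks of anesthesia. For harms of this kind, the stronger the case that the device or surgery was responsible, the less the table offers a label.

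The device is a central safety question here. Section 1.1 says that the second port was introduced because complications with the first exceeded expectation. The split by degree of relatedness is one of the planned displays of device and procedure harm. The rating is made when the event is recorded, so the definition has to be right in the protocol; an analysis plan can only tabulate what was entered.

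**Working it through.** No figure in the plan can be reproduced on this point. The check sets the conditions of Table 7-4 against concrete cases, taking timing and biologic plausibility as met throughout.

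| Case | Competing cause | Dechallenge response | Recurrence | *Possibly* | *Probably* | *Definitely* |
|---|---|---|---|---|---|---|
| A. Permanent cord damage at implantation | no | no | no | fails | fails | fails |
| B. Same injury, another cause plausible | yes | no | no | met | fails | fails |
| C. Death from a complication of revision surgery | no | no | no | fails | fails | fails |
| D. Single device reaction that resolves after explantation | no | yes | no | fails | met | fails |

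Step by step:

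1. **Case A.** There is no competing cause, so *Possibly* is not met. Nothing improves on withdrawal, so *Probably* is not met. Nothing recurs, so *Definitely* is not met. *Not Related* is not met either, because the event is not unrelated to the device and its surgery. No label applies.
2. **A against B.** Adding a competing cause weakens the causal case, yet it moves the event from no label to *Possibly*. The order is inverted.
3. **Case C** fails for the same reasons as A.
4. **Case D** marks the limit of the gap. The *Probably* row does not restrict dechallenge to medication, so removing the device can serve. Being a single event rules out *Definitely* only.
5. **Evidence with no place in the table.** Section 6.3.1 says the definitive cause of a device failure may not be known until exploratory surgery. Section 11.8 has device failures reviewed with the manufacturer's investigation of returned devices. Neither kind of evidence can raise a rating under Table 7-4.

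**Size.** Section 10.2 gives a maximum of 12 patients. If the table reports patient percentages over everyone enrolled, one patient is at least 100/12 = 8.3 percentage points, and more in a table restricted to one device. The protocol gives no rate for irreversible or fatal device events, so the number of ratings affected cannot be stated.

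**The case against.** Three stronger conclusions are tempting, and the objections to each stand.

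**That any single-occurrence device or surgical event falls in the gap.** It does not, as case D shows. IT dosing is also repeated every 28 days (6.3), and revisions may occur up to twice in 6 months (7.12.1), so recurrence can sometimes be observed. The gap is confined to events with no dechallenge response, chiefly irreversible or fatal ones. Nor would counting combinations of the table's conditions measure its size: fixing dechallenge and recurrence as absent presupposes the answer, and the counts carry no frequencies.

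**That the related-event tables miss such events.** To drop out, an event would have to be rated *Not Related*, whose definition it also fails. Other capture is independent of the degree of relatedness: all adverse events are recorded (7.22.1.1); serious events are reported whatever their relationship (7.22.5.1); device failures leading to scheduled revision are serious events, and unanticipated device effects have their own test (7.22.1.5); the eCRF has options for each source (7.22.5.2); and device failures have their own form (7.22.1.4) and, for the SOPH-A-PORT, their own analysis (10.6.2.1).

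**That the stopping rule fails to trigger.** Section 7.24 rests on the sponsor's judgement, whereas Table 7-4 is applied by the investigator. It does not cite the table and treats the three labels alike, so a wrong degree among them changes nothing. It names only study drug and the device, so a purely surgical or IT-process harm lies outside it by its own wording.

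It can also be said that investigators will use sense and choose a related label. They probably will, but then the definitions in use are not the ones written, and they may differ between sites.

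**Conclusion.** The point holds in a limited form. Table 7-4, read as written, gives no degree of relatedness to an irreversible or fatal device or surgical harm that has reasonable timing, no alternative explanation and no dechallenge response. It gives *Possibly* to the same harm when a competing cause exists, and it bars *Definitely* for anything that does not recur. The consequence is a wrong or undefined degree in the device and procedure tabulations of section 10.6.1.1, not loss of the event. The link to section 7.24 is only that it borrows labels defined nowhere else in the protocol.

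This rests on reading the conditions within each row as all required, which is how they are worded. It is a stated rule that gives the wrong answer, not a detail left open. It should be corrected, although analyses that do not use the degree of relatedness are unaffected.

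**What to change.** 1. Keep the dechallenge and rechallenge wording for study drug.
2. For device, device surgical procedure and IT administration process, define the degrees separately, each with reasonable timing and with no need for dechallenge or recurrence:
   - *Possibly*: other causes also plausible.
   - *Probably*: other causes unlikely.
   - *Definitely*: direct evidence, such as imaging, an operative finding or the returned-device investigation under 11.8. Resting this row on evidence, not on the absence of alternatives, keeps it distinct from *Probably*.
3. State for all four sources that an irreversible or fatal event need not show dechallenge or recurrence.
4. Have section 7.24 say which definitions its labels use.

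The cost is protocol wording and revised eCRF completion guidance, with no new data. The drawback is regrading: events already recorded, in at most 12 patients, would be re-rated in an open-label study with outcomes known. If that is done, the ratings already on file should be kept and shown beside the new ones.

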7.22.5 Procedures for Recording and Reporting Adverse Events

7.22.5.1 Reporting Serious Adverse Events Related to Study Procedures

Any SAE regardless of relationship to investigational product, device, device surgical procedure, or IT administration process that occurs in a patient after informed consent (and assent if applicable) should be recorded by the clinical site on an SAE form that is to be transmitted to the Shire Medical Monitor and to the Shire Pharmacovigilance and Risk Management Department at the contact number provided below. The SAE must be completely described on the patient's eCRF, including the judgment of the investigator as to the relationship of the SAE to the investigational product and or device. The investigator will promptly supply all information identified and requested by the sponsor (and/or contract research organization [CRO]) regarding the SAE as to the relationship of the SAE to study drug, device, or procedure.

The investigator must report the SAE to the Shire Pharmacovigilance and Risk Management Department AND to the Shire Medical Monitor on an SAE form. The SAE form must be completed and FAXED or scanned and EMAILED (PDF sent by e-mail) within 24 hours of the investigator's learning of the event to:

Shire Pharmacovigilance and Risk Management Department:

International FAX: [REDACTED] **United Kingdom OR**

United States FAX: [REDACTED]

Email: [REDACTED]

AND

Shire HGT Medical Monitor:

FAX: [REDACTED] **(United States)**

The investigator may also call the medical monitor directly (optional):

Shire HGT Medical Monitor: [REDACTED] **DO**

Shire HGT

Work: [REDACTED]

Cell: [REDACTED] **(24 hour access)**

Email: [REDACTED]

AND

Clinical Project Manager CC'd: [REDACTED]

Any follow-up information must also be completed on an SAE form and faxed or scanned to the same numbers or e-mail address listed above.

In the event of a severe and unexpected, fatal, or life-threatening SAE, the clinical site must contact the Shire Medical Monitor by telephone; this is in addition to completing and

transmitting the SAE form as stated above. The following provides contact information for the Shire Medical Monitor.

If an SAE is assessed as severe and unexpected, or life-threatening, contact:

[REDACTED] DO [REDACTED] Shire Human Genetic Therapies, Inc. [name] [name] Telephone: [REDACTED] Fax: [REDACTED] (United States) Mobile: [REDACTED] (24-hour access)

The investigator must promptly report all required information to the Institutional Review Board (IRB)/Independent Ethics Committee (IEC). It is the responsibility of the sponsor to ensure that each investigator receives a copy of any CIOMS I/MedWatch report that has been submitted to the appropriate regulatory agencies notifying them of an unexpected related SAE. The investigator or sponsor must ensure that the IRB/IEC receives a copy of the report and that a copy is also filed within their study files. In addition, the sponsor will also notify the investigators and IRBs/IECs of all deaths that occur during the study, irrespective of relationship to study medication.

